10.8 Prior and Concomitant Medications

Prior and concomitant medications and treatments will be collected at the time of enrollment and throughout the study. All prior treatments and treatment regimens for SLE and LN will be collected.

10.8.1 Permitted Therapies

Other than restricted medications described in Section 10.8.2, subjects may continue to take their chronic medications.

10.8.2 Restricted Medications

Treatments for SLE and its complications may need to be kept stable, washed out, or may be disallowed.

10.8.2.1 Glucocorticoids

[figure not shown]
In subjects in the Type A cohorts, the dose of glucocorticoids must be kept stable during the study

[figure not shown]
Subjects in the Type B Cohort should be on a stable dose of MMF or MPA for the duration of the study. For subjects that are undergoing induction treatment, they may require additional pulse steroid treatment and receive methylprednisolone ≥500 mg or equivalent within 12 weeks prior to starting study treatment or receive a dose start on Day 1 and Day 2 and then undergo a rapid oral corticosteroid taper, which will be reduced by 20% per week targeting to reach prednisone of approximately <10 mg per day by Week 10. Prednisone or equivalent can be maintained at 7.5 mg per day for the duration of the study

[figure not shown]
Investigators will adhere to the protocol steroid taper schedule unless a safety concern (including

[figure not shown]
Equillium, Inc.	Clinical Study Protocol No. EQ001-19-002	Page 62 of 110

concern related to insufficient response) necessitates departures from the schedule. Such planned departures must be discussed with the Medical Monitor, preferably in advance of the change in medication.

10.9 Enrollment

It is the investigator's responsibility to ensure that subjects are eligible to participate in the study prior to enrollment and continue to remain eligible throughout the study. An IWRS will be used to ensure study drug inventory, accountability, and appropriate cohort allocation.

The study will be open label. After informed consent has been obtained, all screening procedures have been assessed, and study eligibility has been confirmed, subjects will receive EQ001 on Study Day 1. Subjects will be formally enrolled into the study on Day 1, as defined by completing the enrollment transaction within the IWRS.

The study pharmacist (or the designated site staff) will access the IWRS to receive the dose of study drug assigned, record drug accountability, and request resupply.

Equillium, Inc.	Clinical Study Protocol No. EQ001-19-002	Page 66 of 110

Equillium, Inc.	Clinical Study Protocol No. EQ001-19-002	Page 67 of 110
-		

11 STUDY PROCEDURES

The following assessments will be conducted during screening and at the time points specified in the Schedule of Events (SOE) (Section 5.2, Section 5.3, and Section 5.4) and protocol Section 10. All missed visits must be documented in the subject's medical record and the appropriate eCRF.

11.1 Screening and Informed Consent

Each subject must sign and date the informed consent form (ICF) before participating in any study-specific activities. The ICF may be signed up to 4 weeks prior to the Screening Visit for Type A Cohort subjects and 8 weeks prior to the Screening Visit for Type B Cohort Subjects.

After the ICF is signed, the subject will be assigned a unique subject identification number by IWRS.

The subject number, assigned at the time of screening, will be used to identify the subject during the study and must be used on all study documentation related to that subject. The subject identification number will remain constant throughout the entire study and must not be changed after initial assignment. Each study site will maintain a list identifying all subjects by subject identification number and subject initials.

After completing the Screening Period, the subject will be evaluated by the investigator to confirm eligibility. A subject is considered to have started screening on the date that the Screening Visit is recorded in the IWRS. Screen failure subjects will be entered into the IWRS. Investigators will maintain a screening log of all potential study subjects that includes limited information about each candidate, including dates of screening and procedures, and the outcome of the screening process (e.g., enrolled into the study, reason for ineligibility, or withdrawal of consent).

At Baseline and before any study drug is administered, potential subjects will be reviewed by the site to reconfirm their eligibility.

11.2 Demographics and Medical/Surgical History

11.2.1 Demographics

Demographic data will be collected, including each subject's sex, age, race, and ethnicity. Where local regulations do not permit certain demographic data to be collected, collection of those data will not be required.

11.2.2 Medical and Surgical Histories

The investigator or designee will collect the subject's medical and surgical histories, including information on the subject's concurrent medical conditions. All findings will be recorded on the medical history and surgical history eCRFs. A *complete medical history* at the Screening Visit

_		
_		

Clinical Study Protocol No. EQ001-19-002

Page 68 of 110

11.3 Physical Examination

Equillium, Inc.

The investigator or designee will conduct a complete physical examination as outlined in the SOE. Physical examination clinically significant findings prior to the first dose of study drug administration will be recorded on the medical history eCRF; clinically significant findings after the first study drug dose will be recorded as AEs.

11.4 Vital Signs

The following vital sign measurements will be performed: systolic and diastolic blood pressure, pulse, respiration rate, and temperature. Vital signs will be measured according to the SOE. On study drug dosing days, vital signs will be measured prior to the injection and approximately 15 and 30 minutes following the end of the injection. The subject must be seated or in a semi-recumbent position in a rested, calm state for at least 3 minutes before vital signs are collected. The position selected for a subject should be the same throughout the study and documented on the vital signs eCRF whenever possible. Height will be measured without shoes at Screening.

Weight without shoes will be obtained at Screening. On dosing days, weight will be obtained before dosing. The weight at Screening will be used to calculate all study drug doses, unless there has been a weight change of $\geq 20\%$ from Baseline.

11.5 SLEDAI-2K Assessment

The investigator and/or appropriately qualified designee will complete the SLEDAI-2K data collection sheet at specific time points, as specified in the SOE. The same individual should perform all SLEDAI-2K assessments for a given subject whenever possible.

11.6 Urine Protein Creatinine Ratio

The UPCR from a urine collection will be assessed at the timepoints specified in the SOE.

Equillium, Inc.	Clinical Study Protocol No. EQ001-19-002	Page 69 of 110
-----------------	--	----------------

[figure not shown]
11.7 12-Lead Electrocardiography

12-Lead ECGs will be centrally read and obtained on standardized ECG equipment supplied for the study. The subject must be in a semi-recumbent or supine position in a rested, calm state for at least 10 minutes before ECG assessment is performed. Each 12-lead ECG should be performed prior to blood draws, dosing, or other invasive procedures whenever possible.

The investigator or designated study site physician will review, sign, and date all ECGs.

Any clinically significant abnormal ECG findings will be recorded as an AE.

[figure not shown]
11.8 Patient-Reported Outcomes Measures

11.9 Physician Global Assessment

At the visits during which the PGA is assessed, investigators will score their global assessment of disease activity after reviewing the most recent laboratory results and completing the physical examination but before completing the SLEDAI-2K. The same investigator or sub-investigator should complete all the physician global assessment for a given subject whenever possible.

11.10 Kidney Biopsy (if needed and approved)

Equillium, Inc.	Clinical Study Protocol No. EQ001-19-002	Page 70 of 110

11.11 Clinical Laboratory Tests

11.11.1 Safety Laboratory Tests

Blood and urine samples will be collected according to the SOE (Section 5.2, Section 5.3, and Section 5.4) and below. All scheduled laboratory tests, other than urine pregnancy testing and laboratory testing to evaluate hematology parameters prior to dosing, will be performed at the central or local laboratory. The pre-dose laboratory evaluations (ie, hematology for ALC) may be performed at a local or central laboratory up to 14 days prior to the next target dosing day or on the target dosing day. Blood testing for TB may be performed locally, at the investigator's discretion. Repeat laboratory testing will not be required if a test was already performed within the specified time window for collection. Samples may be analyzed for the tests outlined in this protocol and for any additional tests (with the Sponsor's approval) necessary to further evaluate subject safety. These may include, but are not limited to, investigation of unexpected results. Subjects will be in a seated, semi-recumbent, or supine position during blood collection. Collection procedures are described in the study Laboratory Manual.

Equillium, Inc.	EQ001-19-002 Page 71 of 110	Clinic	Equillium, Inc.
Equillium, Inc.	EQ001-19-002 Page 71 of 1	Clinic	Equillium, Inc.

11.11.1.1 Complement and Anti-dsDNA

Blood samples will be assayed for complement C3 and C4 and anti-dsDNA at selected time points (see SOE for details). Total hemolytic complement (CH50) may also be measured in the Type B Cohort.

11.11.1.2 Autoantibodies

[figure not shown]
Serum will be assayed for autoantibodies, including anti-nuclear antibodies (ANA) at selected time points (see SOE for details). Anti-C1q antibodies may also be analyzed.

11.11.1.3 Pharmacokinetics

Serum will be assayed for EQ001 concentrations using a validated assay. The PK samples will be collected at time points specified in the SOE.

11.11.1.4 Anti-Drug Antibody and Neutralizing ADA

Serum samples will be obtained for detection of ADA against EQ001 at the time points specified in the SOE, and, if required, a neutralizing ADA assay will be performed on the same samples. ADA sampling may be requested by the Sponsor at an unscheduled visit to further evaluate safety in individual patients.

Equillium, Inc.	Clinical Study Protocol No. EQ001-19-002	Page 72 of 110
 		
		1
		_

Equillium, Inc.	Clinical Study Protocol No. EQ001-19-002	Page 73 of 110

Page 74 of 110

12 ADVERSE EVENTS

An AE is defined as any unfavorable and unintended sign (including an abnormal laboratory finding), symptom, or disease or any worsening of a pre-existing condition temporally associated with the use of a study drug, whether or not related to study drug. The AEs that occur after the first dose of EQ001 or during the study treatment and safety follow-up periods will be documented on the AE eCRF. The investigator will assess AE severity and the causality relationship of the AE to study drug. The investigator will treat the subject as medically required to ensure the subject's safety.

Laboratory values that are outside the laboratory reference range should be reported as AEs only if the investigator considered those AEs to be clinically significant.

From the time of signing the ICF through the first study drug administration, all SAEs and nonserious AEs related to protocol-mandated procedures (including medication washout performed specifically for the study) will be recorded on the SAE/AE eCRF. All other untoward medical occurrences observed during screening, including exacerbation or changes in the medical and surgical history, will be captured on the medical and surgical history eCRF. Details on recording and reporting AEs are provided below. All AEs will be captured through the last required Follow-up visit or the ET Visit, whichever is later.

Investigators should use their clinical judgment to determine whether a subject is to be withdrawn due to an AE. In the event the subject discontinues study treatment or is withdrawn from the study due to an AE, the subject should be asked to complete all remaining FU study visits. In the event a subject is withdrawn from the study, an ET Visit should be completed.

All subjects experiencing AEs, including clinically significant abnormal laboratory values, whether or not associated with the study drug, must be monitored until the condition (1) returns to normal, (2) returns to the subject's baseline, (3) the investigator determines the AE has reached a stable outcome and is no longer clinically significant, or (4) the subject is considered lost to follow-up.

12.1 Severity

All AEs, both serious and nonserious, will be assessed for severity using the NCI CTCAE v 5.0. The CTCAE scale includes unique clinical descriptions of AEs categorized by anatomy and/or pathophysiology. Reference the following website:

 $https://ctep.cancer.gov/protocolDevelopment/electronic_applications/docs/CTCAE_v5_Quick_R\\ eference~8.5x11.pdf$

The CTCAE scale displays Grades 1 through 5 with unique clinical descriptions of severity for each AE (including abnormal laboratory values), based on this general guideline provided in the scale. For AEs not covered by CTCAE, the conventional definition of severity will be used, as follows:

Equillium, Inc.	Clinical Study Protocol No. EQ001-19-002	Page 75 of 110	

- Grade 1 (mild) AE: Minor; no specific medical intervention; marginal clinical relevance.
- Grade 2 (moderate) AE: Minimal intervention; local intervention; noninvasive intervention.
- Grade 3 (severe) AE: Significant symptoms requiring hospitalization or invasive intervention.
- Grade 4 (life-threatening or disabling) AE: Complicated by acute, life-threatening complications; need for intensive care or emergent invasive procedure.
- Grade 5: Fatal AE

12.2 Causality Assessment

The investigator or qualified subinvestigator is responsible for assessing and assigning the causality relationship of the event to study drug or study-related procedures (e.g., invasive procedures, such as venipuncture) using clinical judgment and the following categories of relatedness:

- Related: There is at least some possibility that the AE could be related to study drug or a study-related procedure.
- Not related: There is a high degree of certainty that the AE is NOT related to study drug or a study-related procedure.

In making a causality assessment of an AE, it should be considered as to whether or not the AE is expected to occur due to the underlying disease, based on the investigator's clinical experience in managing SLE (Section 12.5.1).

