12.5 Reporting Adverse Events

12.5.1 Reporting Procedures for Nonserious Adverse Events

The investigator is responsible for ensuring that all AEs observed by the investigator or designee or reported by the subject are reported using the AE eCRF.

The investigator will assign the following AE attributes:

- AE diagnosis or syndrome(s), if known (if not known, signs or symptoms)
- Dates of onset and resolution (if resolved)
- Severity
- Causality relationship to study drug or study-related procedures
- Action taken
- Outcome

Equillium, Inc.	Clinical Study Protocol No. EQ001-19-002	Page 77 of 110	

Follow-up of nonserious AEs will continue through the last day on the study and/or until a definitive outcome (e.g., resolved, resolved with sequelae, lost to follow-up) is achieved.

When a subject is withdrawn from the study because of a nonserious AE, the Sponsor and/or designee must be notified by email or phone within 48 hours.

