12.5.2 Reporting Procedures for Serious Adverse Events

The investigator is responsible for ensuring that all SAEs observed by the investigator or reported by the subject are promptly assessed and reported to the Sponsor and/or designee. The investigator must assess the causality relationship of the SAE to study drug or any study-related procedure.

The procedures for reporting SAEs are as follows:

- Within 24 hours of the investigator's knowledge of the event, enter data into the AE/SAE eCRF. If the EDC is not available, the paper SAE Report Form may be used, but all data must be entered into the EDC once the EDC is available.
- Additional contact numbers and AE/SAE reporting instructions will be provided in the eCRF Completion Guidelines.
- For fatal or life-threatening events and all SAEs, also email and/or fax redacted copies of
 hospital records, autopsy reports, and other documents, when requested and applicable.
 Transmission of such documents should occur with personal subject details de-identified
 (redacted), without losing the traceability of a document to the subject identifiers. Entry
 of the initial report of the event into EDC should not be delayed in order to include these
 additional documents.
- The Sponsor and/or designee may request additional information from the investigator to ensure the timely completion of accurate safety reports.

The investigator must take all necessary therapeutic measures for resolution of the SAE. Any medications or therapies necessary for treatment of the SAE must be recorded in the event description section of the SAE form and the concomitant medication eCRF.

[figure not shown]
Follow-up of SAEs will continue through the last day on the study and/or until a definitive outcome (e.g., resolved, resolved with sequelae, lost to follow-up, fatal) is achieved.

[figure not shown]
While pregnancy is not considered an AE, all cases of fetal drug exposure via a maternal parent as study subject or pregnancy of a partner of a male study subject that occurs during the study or within 130 days after the last dose of study drug will be reported immediately to the Sponsor or its designee. Information related to the pregnancy must be documented on a Pregnancy Confirmation and Outcome Form, provided by the Sponsor or its designee, and the pregnancy should be followed until a definitive outcome has been determined.

Equillium, Inc. Clinical Study Protocol No. EQ001-19-002 Page 78 of 110

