 - Any TEAE leading to study drug discontinuation
 - Any TEAE leading to death

AESIs include injection site-related reactions > Grade 3, lymphopenia > Grade 3 and fever and other injection related (hypersensitivity) reaction > Grade 3, and anaphylaxis.

- TEAEs by SOC and PT
- TEAEs Related to Study Drug by SOC and PT
- TESAEs by SOC and PT
- TESAEs Related to Study Drug by SOC and PT
- TEAEs with Severity Grade ≥ 3 by SOC and PT
- TEAEs by SOC, PT and Maximum Severity Grade
- TEAEs Leading to Study Drug Discontinuation by SOC and PT
- TEAEs of Special Interest by SOC and PT

TEAEs of Special Interest by SOC_PT and Maximum Severity Grade

A by-subject listing of AE data will also be created. Adverse events occurring within 30 days after last dose of study drug and AEs occurring >30 days after the last dose of study drug through the end of the study will be separately summarized. All AEs will be included in the listings. AEs occurring before start of study treatment will be included in the data listings but will not be included in the summary tables of AEs.

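### Protocol 12.2 rates drug and procedure causality in one 'Related' category, but the SAP's related-event tables need relationship to study drug alone

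*Protocol*

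**What the plan says.** The documents describe causality in two ways.

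**Two causes in one answer.** Protocol 12.2 offers two categories and gives venipuncture as an example of a procedure.
- 'Related' is defined as: "There is at least some possibility that the AE could be related to study drug or a study-related procedure".
- 'Not related' is defined as: "There is a high degree of certainty that the AE is NOT related to study drug or a study-related procedure".
- Protocol 12.5.1 lists a single causality attribute for each event: "Causality relationship to study drug or study-related procedures".
- Protocol 12.5.2 does the same for serious events: "The investigator must assess the causality relationship of the SAE to study drug or any study-related procedure".

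**Drug only.**
- The opening of Protocol 12 says: "The investigator will assess AE severity and the causality relationship of the AE to study drug".
- Protocol 13.7 summarises adverse events by their relationship to study drug.
- Protocol 14.7 requires the progress notes to carry the investigator's view of the relationship to study drug.
- SAP 10.3 plans overall-summary rows for treatment-related TEAEs and TESAEs, a table titled "TEAEs Related to Study Drug by SOC and PT", and the matching table for TESAEs. It also treats an event with missing relatedness as drug-related.

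No visible passage says how the 12.2 answer becomes the drug-only answer that the tables need. The eCRF is not among the documents, and the content of SAP 6.2 (Key Definitions) is not visible.

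**The concern.** A table headed as drug-related should contain only events that the investigator could not confidently separate from the drug. The 12.2 categories do not deliver that. An investigator who is certain that EQ001 played no part, but thinks a blood draw did, has only 'Related' to choose.

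Safety and tolerability is the primary objective. The study is open label and every subject receives EQ001 (Protocol 8.4), so there is no control arm to show the background rate of procedural events. Investigator attribution is therefore one of the few tools for sorting drug effects from the rest. If it mixes two causes, the related tables no longer say what their titles claim.

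**Working it through.** **Step 1. Compare the two definitions case by case.** Take the two judgements an investigator can make about one event.

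| Drug possible? | Procedure possible? | Category under Protocol 12.2 | Belongs in SAP 10.3 drug-related tables? |
|---|---|---|---|
| yes | yes | Related | yes |
| yes | no | Related | yes |
| no | yes | Related | **no** |
| no | no | Not related | no |

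The definitions disagree in the third row only. There the merged category adds an event and never removes one, so any error is an over-count.

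**Step 2. Which events reach the tables.** SAP 10.3 tabulates events that start after dosing, or that start earlier and worsen after exposure. Events before the start of treatment are listed but not tabulated. A procedural event therefore matters only if it starts or worsens after the first dose. A haematoma from a blood draw at a later visit qualifies.

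**Step 3. The condition.** The third row reaches the tables only if the database holds one causality answer filled in as 12.2 describes. With separate drug and procedure fields, and tables built on the drug field, it does not.

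**Step 4. What does not depend on the answer.** The primary endpoint (Protocol 8.6.1, SAP 4.1) is defined without reference to causality, so the TEAE and TESAE totals stay as they are. The DLT definition (Protocol 8.8.2) has its own test, which asks about the study drug alone.

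**Step 5. Scale.** The plan states no figure to reproduce. Let n be the group size, x the subjects with a truly drug-related TEAE, and k the subjects whose only 'Related' TEAE is procedural. The rise in incidence is (x + k)/n − x/n = k/n. Group sizes come from Protocol 8.1. For k = 1:
- Type B, n = 20: 1/20 = 5.0 points
- one Type A cohort, n = 6: 1/6 = 16.7 points

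Starting from x = 0, the Clopper–Pearson 95% intervals are as follows. They are calculated here for scale; SAP 10.3 plans only counts and percentages.
- n = 20: 0/20 (0 to 16.8%) becomes 1/20 (0.1 to 24.9%)
- n = 6: 0/6 (0 to 45.9%) becomes 1/6 (0.4 to 64.1%)

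The value of k is not in the documents. In an overall row, k excludes any subject who has another 'Related' TEAE. In a preferred-term row, where SAP 10.3 counts a subject once per term, only another 'Related' event of the same term excludes the subject.

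**The case against.** **The conduct of the study may already be drug-specific.** Protocol 12, 13.7 and 14.7 all speak of relationship to study drug, and the SAP's rule for missing relatedness suggests a drug-specific variable. The 'or' in 12.2 could mean two objects, each rated separately. This is a fair reading, and without the eCRF it cannot be excluded. It makes the harm conditional. It does not remove the inconsistency: with one field the tables are mislabelled, and with two fields 12.2 and 12.5.1 misdescribe the assessment and the SAP should name the field it uses.

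**The error is cautious and easy to spot.** It runs toward over-attribution, as do the SAP's worst-case rules for missing data, and a reader of the preferred-term tables and listings may recognise a puncture-site haematoma. This limits the consequence. It does not make a drug-related count correct when events the investigator ascribed to a procedure are in it.

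**Type A is largely past.** Under SAP 2.2 Type A enrolment is complete and its data have been frozen and analysed. New protocol wording cannot change how those events were assessed. This stands, so the practical value lies mainly in Type B.

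**The washout reading.** A reader might infer that lupus flares after a study washout would be counted against the drug. Protocol 12 does refer to "AEs related to protocol-mandated procedures (including medication washout performed specifically for the study". That sentence uses a different term from 12.2 and governs what is recorded between consent and first dose. It is not a causality rule for later events, and 12.2 illustrates procedures with invasive ones. The flare would also have to start or worsen after dosing. The documents do not carry the inference that far.

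**Conclusion.** The inconsistency is real and worth removing before the final analysis. Protocol 12.2, 12.5.1 and 12.5.2 merge two causes that the analysis needs apart. Following the text literally, with one causality field, counts procedure-only events that start or worsen after the first dose as drug-related. The effect is confined to the related breakdown of TEAEs and TESAEs and can only raise it, by 5.0 points per affected subject at n = 20 and 16.7 points at n = 6. Whether any subject is affected is unknown.

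Three stronger conclusions are tempting and not supported:
- That the primary endpoint is inflated. Its counts carry no causality restriction.
- That dose escalation or the MTD is compromised. The DLT test asks about the study drug alone.
- That the drug-related rate is overstated by some stated amount, for example 15 points from three subjects of 20. The documents give no count of such subjects.

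**What to change.** 1. **Protocol 12.2, 12.5.1 and 12.5.2.** Reconcile them with 12 and 13.7 by asking for two separate yes/no answers: related to EQ001, and related to a study procedure.
2. **SAP 10.3.** State that the treatment-related rows and the drug-related tables use only the EQ001 answer, and that the missing-relatedness rule applies to that answer. Show procedure-only events in their own row or listing.
3. **If only one field was collected.** Before the final database lock, query every record marked 'Related' for the EQ001 judgement. The progress notes required by Protocol 14.7 should already hold it. Because the study is open label, put the same question for every such record, whatever the event. Type B is the main target; check Type A 'Related' records where feasible, since SAP 2.2 has the final analysis use all data in the database.
4. **If two fields already exist.** Only the wording in items 1 and 2 is needed.

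The cost is a few lines of text and either one extra eCRF field or a short data query. No subjects, visits or procedures are added.
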